### **7.2.1. AG-221 Treatment**

Subjects randomized to the AG-221 treatment arm will receive continuous 28-day cycles of AG-221 100 mg PO QD for 28 days. In addition, subjects may receive BSC per standard institutional practice and as deemed necessary by the investigator. In order to optimally benefit from the AG-221 treatment, the investigator should aim to treat subjects for at least 6 cycles or as long as subjects continue to benefit from the treatment until the End of Trial. Subjects may be discontinued from the treatment for any of the reasons detailed in Section 11.1.

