### **Dose escalation for augmenting treatment responses**

The AG-221 dose for the subsequent treatment cycles that are given may be increased from 100 mg QD to 200 mg QD if the following occurs:

- ANC  $< 0.5 \times 10^9/L$  after being on AG-221 for the first cycle without  $\geq$  Grade 3 AEs suspected by the investigator to be related to AG-221; or
- no partial remission (PR) achieved after being on AG-221 for at least 2 cycles without  $\geq$  Grade 3 AEs suspected by the investigator to be related to AG-221; or
- evidence of morphologic relapse or PD

If benefit is demonstrated with an increased level of dose, then that dose level should be maintained during the subsequent treatment cycles that are given. However, once increased, the AG-221 dose may be reduced if a certain level of toxicity (eg, Section 7.2.1.3) is observed and considered as possibly or probably related to AG-221 treatment. A maximum of 3 steps of AG-221 dose reduction, stepwise first from 200 mg QD to 150 mg QD, second from 150 mg QD to 100 mg QD, and then last from 100 mg QD to 50 mg QD, are permitted in the event of toxicities, depending on the dose that the subject is on. Once reduced, the AG-221 dose should not be re-escalated unless there is evidence of morphologic relapse or PD. Any subject who is unable to tolerate 50 mg QD of AG-221 should be discontinued from study treatment.

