3. Piecewise cox regression will provide hazard estimates for every 6 months;
4. In the presence of non-proportional and early OS separation, a generalized Wilcoxon test will be utilized to compare survival curves.

A number of subgroups analyses will also be carried out. For details see Section 10.4.

Additionally, the primary endpoint will be repeated for a dose level group analysis of AG-221 subjects who had at least one dose > 100mg during the study versus those who received only dose \leq 100mg.

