10.3.1.1. Overall Response Rate

Overall response rate (ORR) is defined as the rate of Best Response in CR + CRi + CRp + partial remission (PR) + morphologic leukemia-free state (MLFS) according to modified IWG AML response criteria.

The ORR will be summarized by treatment group and be compared between arms by the Cochran-Mantel-Haenszel (CMH) test with stratification factors:

- Prior intensive therapy for AML: yes versus no
- Primary refractory: yes versus no
- Prior allogeneic HSCT for AML: yes versus no

If a stratification factor covariate has less than 40 subjects in one of its levels across treatment groups, then this factor will not be used in stratified analysis. This analysis based on IRAC assessment in the ITT population will be used as the main analysis of ORR.

As sensitivity analyses, a CMH test with the above strata will be performed in the mITT population. In addition, a Fisher's exact test without stratification factors will be performed in both ITT and mITT population. An Odds Ratio and its 95% C.I. of responders versus non-responders between treatment arms will also be calculated. This analysis will be repeated for the local assessment of response as a supportive analysis of ORR.

Additionally, overall response rate will be repeated for a Dose group analysis of AG-221 subjects who had at least one dose > 100mg during the study versus those who received only dose ≤100mg.

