10.3.1.2. Event-Free Survival

Event-free survival (EFS) is defined as the period from the date of randomization to the date of documented morphologic relapse (hereafter referred as relapse) after CR/CRi/CRp, PD according to modified IWG AML response criteria or death from any cause, whichever occurs first. Subjects who are alive without any of these events will be censored at the date of their last valid response assessment. Subjects who do not have post-randomization response assessment will be censored at date of randomization.

If a subject begins a new anti-cancer therapy prior to documented disease progression (or death), the subject will be censored at the date of last assessment before starting the new anti-cancer therapy. Subjects with two or more consecutive missing response assessments prior to documented progression (or death) will be censored at the last date of response assessment before the missing assessments.

Analysis of EFS will be similar to the analysis of OS. The stratified log-rank test based on the ITT population will be considered the primary analysis for EFS, with unstratified analyses and the analyses based on mITT populations considered supportive analyses. The analysis based on local assessment of response will be conducted as a supportive analysis of EFS.

Additionally, EFS will be repeated for a Dose group analysis of AG-221 subjects who had at least one dose > 100mg during the study versus those who received only dose ≤100mg.

Table 4: Censoring Rules for EFS

Value of Event-free Survival Date (ADT)	Censored (Y,N)	Derivation
ADT = min(death date, relapse date, progression date)	N	If a subject died, relapsed, or had disease progression by independent review, and the subject has less than two consecutive missing response assessments prior to a visit documented death, relapse, or progression which is before any subsequent anti-cancer therapies
ADT = the last event-free assessment date before missing assessments/ randomization date	Y	If a subject died, relapsed, or had disease progression by independent review, and the subject has two or more consecutive missing response assessments prior to a visit documented death, relapse, or progression
ADT = the last assessment date/randomization date	Y	If a subject did not die, or did not have relapse or progression, and did not receive any subsequent anti-cancer therapies. If there was no post-randomization response assessment, then ADT = the randomization date.

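### The AG-221 dose-level comparisons of OS, ORR and EFS group subjects by a status acquired after randomization, so a difference can appear with no dose effect.

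*SAP*

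**What the plan says.** SAP 10.2 plans for the OS analysis to be "repeated for a dose level group analysis of AG-221 subjects who had at least one dose > 100mg during the study", set against AG-221 subjects who stayed at or below 100 mg. SAP 10.3.1.1 adds that "overall response rate will be repeated for a Dose group analysis of AG-221 subjects" on the same split, and 10.3.1.2 that "EFS will be repeated for a Dose group analysis of AG-221 subjects who had at least one dose > 100mg during the study". OS and EFS are both measured from randomization (SAP 10.2 and 10.3.1.2). None of the three sections gives a landmark, a time-dependent definition, a weighting method or a caveat.

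The starting dose is common to all: "Subjects randomized to the AG-221 treatment arm will receive continuous 28-day cycles of AG-221 100 mg PO QD for 28 days" (Protocol 7.2.1). Protocol 7.2.1.2 allows an increase only for subsequent cycles, on one of three grounds:

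- ANC below 0.5 x 10^9/L after the first cycle;
- "no partial remission (PR) achieved after being on AG-221 for at least 2 cycles";
- "evidence of morphologic relapse or PD".

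The first two also require that the subject has had no event at or above the level described as "Grade 3 AEs suspected by the investigator to be related to AG-221".

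SAP 11.1 treats dose differently for safety: its dose-cohort tables assign each adverse event according to the dose history before the event.

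**The concern.** A subject is not above 100 mg at randomization. The subject becomes so by living long enough on treatment, by failing to respond or by progressing, and, for two of the three triggers, by tolerating the drug. Comparing ever with never from time zero then mixes three selections:

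- **Survival.** Time before escalation is guaranteed survival for the escalated group. Deaths in that time can only be counted in the other group.
- **Response and progression.** Non-response and relapse/PD send subjects with worse prognosis into the higher-dose group. For ORR, response status helps to decide the group. For EFS, the third trigger overlaps with the event being analysed.
- **Tolerability.** Subjects with related Grade 3 or higher events are kept out of the higher-dose group under the first two triggers.

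At stake is the interpretation of the dose-level tables. A reader could take a difference in them as evidence for or against a benefit of the higher dose when no such effect exists.

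**Working it through.** **1. The plan's own model.** The documents give no figure for the dose-level analyses, so I first checked that the design model reproduces. Inputs (SAP 4.4, 12.2): medians 5.6 and 8 months, exponential, HR 5.6/8 = 0.7, two-sided alpha 0.05, 80% power, interim at 163 deaths.

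- Fixed design: 4 x (1.960 + 0.842)^2 / (ln 0.7)^2 = 247 deaths.
- With one Lan-DeMets O'Brien-Fleming interim: 249.7, that is 250 as stated, with boundaries 0.0055 (HR 0.6715) and 0.0233 (HR 0.7775) as stated.

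The same model can be used for the AG-221 arm.

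**2. Deaths before escalation is possible.** A cycle is 28 days and a month 30.4375 days (SAP 15.1.1), so a cycle is 28/30.4375 = 0.920 months.

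- End of Cycle 1: 1 - 0.5^(0.920/8) = 7.7%; 0.077 x 158 = about 12 subjects.
- End of Cycle 2: 1 - 0.5^(1.840/8) = 14.7%; 0.147 x 158 = about 23 subjects.

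Suppose a share p of Cycle 2 survivors escalates then (p is an assumption; the documents give none). Mortality up to that point is 0% above 100 mg and 0.147 / [0.147 + 0.853 x (1 - p)] in the other group: 17.8%, 22.4% and 30.2% for p = 20%, 40% and 60%.

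**3. OS with no dose effect, escalation unrelated to prognosis.** 2,000 simulated trials of 158 AG-221 subjects, 8-month median, plan accrual, analysis at month 49, drop-out taken as 9% per year (assumption). Entries are for 20% / 35% / 50% escalating.

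| Escalation | Ever/never HR | Log-rank p < 0.05 |
|---|---|---|
| all at Cycle 2 | 0.89 / 0.86 / 0.82 | 6% / 11% / 18% |
| all at Cycle 3 | 0.78 / 0.75 / 0.70 | 14% / 28% / 47% |
| spread over Cycles 2-7 | 0.68 / 0.64 / 0.58 | 26% / 54% / 83% |

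A time-dependent dose term gives 0.99-1.02 on the same data, but only because escalation here carries no prognostic information.

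**4. OS with no dose effect, escalation of non-responders only, at the end of Cycle 2.** Assumed: 30% responders, half of non-responders escalate, response alters the death hazard from then on.

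| Non-responder hazard relative to responders | 1 | 1.5 | 2 | 3 | 4 |
|---|---|---|---|---|---|
| Ever/never HR | 0.76 | 0.86 | 0.93 | 1.03 | 1.09 |
| Unadjusted time-dependent HR | 1.01 | 1.22 | 1.38 | 1.62 | 1.80 |

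With 40% responders whose hazard is lower from randomization onward (35-50% of non-responders escalating), the ever/never HR is 0.78-0.79 if response has no survival value, 1.08-1.10 if responders have half the hazard, and 1.32-1.36 at 0.3 times. Comparing only subjects at risk at the same cycle with the same response status gives 0.99-1.02.

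**5. ORR with no dose effect.** Assumed: 15% of Cycle 2 survivors have responded, 30% of the others respond later, half of the non-responders escalate, and deaths before the end of Cycle 2 count as non-response. With no early responder escalating, the higher-dose group is 0.853 x 0.85 x 0.5 = 0.362 of the arm, with ORR 30.0%. The rest have (0.853 x 0.15 + 0.362 x 0.30) / 0.638 = 37.1%. If 20% of early responders escalate at relapse, the pair is 34.6% vs 34.5%; if 50%, it is 40.5% vs 30.1%.

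**The case against.** The strongest reply is that these are additional displays within one arm. SAP 10.1 confines the multiplicity strategy to AG-221 versus CCR overall, and the SAP nowhere says the split estimates a dose effect. That stands, and it limits the consequence. A reader might infer that the primary result or the OS/ORR/EFS hierarchy is compromised; it is not.

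A reader might also infer that the split is biased in favour of the higher dose because of the guaranteed survival time. The documents do not support a direction. They give no escalation rate or timing, no responder share and no prognostic value of response, and the sign changes within plausible assumptions.

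Nor is relapse/PD as an escalation trigger simply the EFS event. SAP Table 4 counts an event "If a subject died, relapsed, or had disease progression by independent review", that review is retrospective and blinded (Protocol 6.5.1), and PD needs confirmation (Protocol Appendix F). The overlap is real but partial, and its size for EFS is not quantified here. Similarly, ORR counts MLFS while the second trigger refers to PR, so some responders might still qualify for escalation. The ORR figures above do not model this.

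It might be argued that SAP section 10 already excludes p-values, since it describes comparisons of AG-221 with CCR. It does not say that only those will be made, and 10.2 says the primary analysis is repeated. Whether tests will be reported is open.

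Finally, a time-dependent dose term looks like the standard cure. Alone it is not: in step 4 it lies further from 1 than the ever/never split whenever the non-responder hazard is 1.5 times or more.

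**Conclusion.** The point holds: as written, the three dose-level analyses can show a difference in either direction with no dose effect. The part that needs no assumption beyond the plan's 8-month exponential median is the early mortality, 7.7% by the end of Cycle 1 and 14.7% by the end of Cycle 2. Deaths before escalation can be counted only in the lower-dose group. Beyond that, the simulated null OS hazard ratio runs from clearly below 1 (0.58) to above 1 (1.36), and the null ORR difference takes either sign. These sizes rest on assumed escalation timing, responder share and prognostic strength of response. They show that the contrast is uninterpretable as a dose effect; they do not predict what this trial will show.

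**What to change.** In SAP 10.2, 10.3.1.1 and 10.3.1.2, state that the dose-group analyses are descriptive, carry no p-values and do not estimate a dose effect.

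- **OS and EFS:** do not compare ever with never from randomization. If a comparison is shown, start the clock at a given cycle. Compare subjects escalated at that cycle with those still at risk and not yet escalated, matched or stratified on response/relapse status and related Grade 3 or higher AE status at that cycle. For EFS, include only escalation before the EFS event. Do not rely on an unadjusted time-dependent dose term: it removes the guaranteed survival time but not the selection by response.
- **ORR:** do not compare the two groups. Among escalated subjects, report response before escalation and new or improved response after it. Note that this is uncontrolled and that late responses to the starting dose cannot be separated out; the protocol's amendment rationale itself notes that response may be delayed.

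The cost is some extra programming on dosing, response and AE data already collected, and a less simple table. Residual confounding remains and should be stated. Dosing, sample size and alpha do not change.

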10.3. Analyses of Secondary Efficacy Endpoints

The time-to-event secondary efficacy variables will be analyzed similarly to the primary efficacy variable with and without stratification when appropriate. KM methods will be used to estimate time-to-event curves, and hazard ratio and its two-sided 95% confidence interval (CI) will be estimated from Cox proportional hazards regression model, unless otherwise specified. Counts and percentages will be used to describe categorical secondary variables.

All secondary efficacy endpoints will be analyzed based on ITT population and key efficacy analysis will be performed on the mITT population as supportive evidence and to assess the robustness of the efficacy findings. Subjects will be analyzed according to randomized treatment group.

Throughout, summaries of Complete Remission will include both CR and CRc responses, and will be displayed as CR. CRc will be summarized separately once, and otherwise will be displayed in combined categories as CR.

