#### 9.6.2.2. Additional Secondary Efficacy Analyses

The other secondary endpoints include duration of response, time to response, rates of overall remission, CR and HI assessed by an IRAC according to modified IWG AML response criteria ([Appendix F](#)) and IWG MDS HI criteria ([Appendix H](#)), treatment mortality at 30 and 60 days, one-year survival, rate of HSCT and time to treatment failure. The definitions of these additional secondary efficacy endpoints are listed below and in Section 2.

**Duration of response** is defined as time from first documented MLFS/CR/CRi/CRp/ PR to documented morphologic relapse after CR/CRi/CRp/ PD or death due to any cause, whichever occurs first. Subjects without morphologic relapse, PD or death due to any cause will be censored at the date of the last response assessment.

**Time to response** is defined as time from randomization to first documented MLFS/CR/CRi/CRp/ /PR. Subjects without a MLFS/CR/CRi/CRp/ PR will be censored at the date of the last response assessment.

**Treatment mortality at 30 and 60 days** is defined as rate of death from any cause within 30 or 60 days of initiation of study treatment.

**One-year survival** is defined as the probability of survival at 1 year from randomization.

**Overall remission rate** is defined as rate of CR + CRi + CRp according to modified IWG AML response criteria ([Appendix F](#)).

**Complete remission rate** is defined as rate of CR according to modified IWG AML response criteria ([Appendix F](#)).

**Hematologic improvement rate** is defined as rate of neutrophil response (hematologic improvement neutrophil response [HI-N]) + platelet response (hematologic improvement platelet response [HI-P]) + erythroid response (hematologic improvement erythroid response [HI-E]) according to IWG MDS HI criteria ([Appendix H](#)).

**Rate of HSCT** is defined as rate of bridge-to-HSCT through study treatment.

**Time to treatment failure** is defined as time from randomization to discontinuation of study treatment due to any cause.

The rate of CR/CR with partial hematologic recovery (CRh; [Appendix F](#)) and duration of CR/CRh will be analyzed using the statistical methods mentioned above or other statistical methods as appropriate. Note: CRh is not available for the investigator's assessment and will be assessed by the Sponsor only and based on laboratory dataset.

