10.3.1. Key Secondary Endpoints

The key secondary efficacy endpoints include ORR and EFS assessed by an Independent Response Assessment Committee (IRAC) and by local investigators based on modified International Working Group (IWG) AML response criteria. Details of the procedure used to proceed IRAC assessed IWG and CR/CRh responses, and the IRAC assessed HI response can be found in the separate IRAC Charter.

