10.3.2.7. Complete Remission Rate

Complete remission rate is defined as rate of CR according to modified IWG AML response criteria per IRAC.

Number and percentage of subjects with complete remission will be summarized by treatment groups. Comparisons between AG-221 and CCR will be analyzed by Fisher's exact test. Investigator assessed results will be summarized as a supportive analysis

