15.5. International Working Group Acute Myeloid Leukemia Response Criteria

Hematologic Response According to modified IWG Criteria for AML	
Category	Definition
Morphologic Complete Remission (CR)	Defined as less than 5% blasts in a BM aspirate sample with marrow spicules and with a count of at least 200 nucleated cells. There should be no blasts with Auer rods and absence of extramedullary disease. Plus, all the following conditions should be met: 
 ANC $\geq 1 \times 10^9/L$ (1,000/μL) Platelet count $\geq 100 \times 10^9/L$ (100,000/μL) Independent of red cell transfusions for ≥ 1 week immediately before each response assessment
Morphologic Complete Remission with Incomplete Neutrophil Recovery (CRi)^a	Defined as all criteria of morphologic CR except the following: 
 ANC $< 1 \times 10^9/L$ (1,000/μL)
Morphologic Complete Remission with Incomplete Platelet Recovery (CRp)^a	Defined as all criteria of morphologic CR except the following: 
 Platelet count $< 100 \times 10^9/L$ (100,000/μL)
Morphologic Complete Remission with Partial Hematologic Recovery (CRh)^a	Defined as all criteria of morphologic CR except the following: 
 ANC $> 0.5 \times 10^9/L$ (500/μL), and Platelet count $> 50 \times 10^9/L$ (50,000/μL)
Morphologic Leukemia-free State (MLFS)	Defined as less than 5% blasts in a BM aspirate sample with marrow spicules and with a count of at least 200 nucleated cells. There should be no blasts with Auer rods and absence of extramedullary disease
Partial Remission (PR)	Defined as all hematologic criteria of morphologic CR with a $> 50\%$ decrease in the percentage of BM blasts to 5% to 25% (a blast count value of $< 5\%$ may also be considered a partial remission if Auer rods are present) ^b
Cytogenetic Complete Remission (CRc)	Defined as CR/CRi/CRp with a reversion to a normal karyotype in cases with an abnormal karyotype at baseline, based on evaluating ≥ 20 metaphase cells from BM
Morphologic Relapse after CR/CRi/CRp^a	Defined as one of the following conditions: 
 Reappearance of $\geq 5\%$ blasts in the BM not attributable to any other cause (e.g., BM regeneration after consolidation therapy); or Development of extramedullary disease
Not evaluable (NE)^a	Defined as without a post-treatment response assessment

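### SAP 10.3 counts every cytogenetic complete remission (CRc) as CR, although a CRc may rest on CRi or CRp, so the reported CR rate can include subjects who fail a CR criterion

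*SAP*

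**What the plan says.** The opening of SAP 10.3 sets a rule for all secondary efficacy summaries: "Throughout, summaries of Complete Remission will include both CR and CRc responses, and will be displayed as CR". The next sentence adds: "CRc will be summarized separately once, and otherwise will be displayed in combined categories as CR".

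The CRc row of SAP 15.5 reads: "Defined as CR/CRi/CRp with a reversion to a normal karyotype in cases with an abnormal karyotype at baseline". Protocol Appendix F gives the same definition.

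In SAP 15.5, CR requires marrow blasts below 5% with no Auer rods and no extramedullary disease, ANC of at least 1 x 10^9/L and platelets of at least 100 x 10^9/L. The subject must also be "Independent of red cell transfusions for" at least one week. The CRi and CRp rows both begin "Defined as all criteria of morphologic CR except the following". The exception is ANC below 1 x 10^9/L for CRi and platelets below 100 x 10^9/L for CRp.

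SAP 10.3.2.7 defines the endpoint: "Complete remission rate is defined as rate of CR according to modified IWG AML response criteria per IRAC". Protocol 9.6.2.2 says the complete remission rate "is defined as rate of CR according to modified IWG AML response criteria". Neither mentions CRc.

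SAP Section 13, which lists changes from the protocol's statistical section, names only the transfusion-independence analysis.

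**The concern.** The endpoint is defined as one response category, but the display rule fills it with two, and the second is not a subset of the first. Two subjects with the same marrow and the same blood counts could be reported differently only because one had an abnormal baseline karyotype that reverted.

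The label CR tells a reader that neutrophils and platelets have recovered. If CRi- or CRp-based CRc is included, that reading is no longer safe, and the Fisher's exact comparison of AG-221 with CCR is made on a numerator other than the defined one. The same applies to the supportive investigator-assessed rate. It also applies to the best-response rows of the transfusion-independence table in SAP 10.3.2.8, which set CR apart from CRi/CRp precisely because count recovery matters there.

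**Working it through.** **1. Definitions side by side** (SAP 15.5; Protocol Appendix F agrees)

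| Category | ANC (x 10^9/L) | Platelets (x 10^9/L) | Other CR criteria | Karyotype |
|---|---|---|---|---|
| CR | ≥ 1 | ≥ 100 | met | not used |
| CRi | < 1 | ≥ 100 | met | not used |
| CRp | ≥ 1 | < 100 | met | not used |
| CRc | as CR, CRi or CRp | as CR, CRi or CRp | met | abnormal at baseline, reverted to normal |

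**2. What each rule counts**

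- Defined complete remission rate (SAP 10.3.2.7, Protocol 9.6.2.2): CR only.
- Displayed rate (SAP 10.3): CR together with CRc.
- Difference: CRi with karyotype reversion, plus CRp with karyotype reversion. No text in the protocol or SAP removes these or returns them to CRi or CRp.

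The displayed rate is therefore never below the defined rate, and it is higher whenever such a response is recorded as CRc.

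**3. Example.** A subject has ANC 0.7 and platelets 120 x 10^9/L and meets every other CR criterion. With a normal baseline karyotype the subject is CRi. With an abnormal karyotype that reverted, the subject is CRc and is shown as CR. The ANC fails the CR threshold in both cases.

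**4. Which results move**

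- Complete remission rate by IRAC, its Fisher's exact test, and the investigator summary: yes.
- CR row of the transfusion-independence table: yes.
- Overall remission rate (CR + CRi + CRp) and ORR (CR + CRi + CRp + PR + MLFS): no, because CRi and CRp already count.
- EFS: no, because relapse is defined after CR, CRi or CRp alike.
- OS: no.

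**5. Size per subject.** The plan states no expected CR or CRc rate, so it has no figure to reproduce. The input is 158 subjects per arm (SAP 4.4).

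- One relabelled subject: 1/158 = 0.63 percentage points on that arm's rate.
- Three: 3/158 = 1.9 points. Five: 5/158 = 3.2 points. Ten: 10/158 = 6.3 points.
- Change in the arm difference = (a − c) x 0.63 points, where a and c are the relabelled subjects in AG-221 and CCR. Two versus one gives +0.63, one versus one gives 0, and one versus two gives −0.63.

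**6. Illustration with assumed counts** (not a prediction; none of these counts is in the documents)

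| Shown as CR, AG-221 vs CCR | Relabelled subjects included | Rates | Fisher p, two-sided |
|---|---|---|---|
| 30 vs 20 | none | 19.0% vs 12.7% | 0.165 |
| 38 vs 22 | 8 vs 2 | 24.1% vs 13.9% | 0.031 |
| 30 vs 22 | 0 vs 2 | 19.0% vs 13.9% | 0.288 |

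The labelling rule can move the nominal p-value in either direction. The table shows nothing about which direction is likely.

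**The case against.** **The Charter may settle it.** SAP 10.3.1 says that details of the procedure for "IRAC assessed IWG and CR/CRh responses, and the IRAC assessed HI response can be found in the separate IRAC Charter". That Charter was not available for this review. If the IRAC records CRc only on top of a full CR, no subject moves in the main analysis. This stands as a limit on what can be said about actual misclassification. It does not repair the SAP, whose own appendix defines CRc more broadly, and nothing in the protocol or SAP restricts CRc for the investigator-assessed summary.

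**Few subjects may qualify.** A subject must be CRi or CRp, have an abnormal baseline karyotype, have follow-up cytogenetics done, and revert to normal on at least 20 metaphases. The number may be small. That limits the size, which is unknown in any case, but not the conflict.

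**The pooling is stated openly and CRc is summarized once on its own.** That summary caps how many subjects shown as CR could be CRi- or CRp-based. No split by underlying category is specified, however, so the defined rate cannot be recovered from it.

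**It is a minor endpoint.** SAP 10.1 limits the testing sequence to OS, ORR and EFS. The same rule applies to both arms and the IRAC is blinded, so no direction of bias is shown. All of this stands, and it is why the consequence is a mislabelled secondary rate rather than a confirmatory error.

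**Conclusion.** The concern holds on the text. SAP 10.3 gives the complete remission rate a numerator wider than its definition in SAP 10.3.2.7 and Protocol 9.6.2.2, and SAP Section 13 does not declare this as a change. It should be corrected.

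Confidence is high that the written rules conflict. How many subjects are affected, and in which arm, is unknown: the documents give no CRi, CRp, abnormal-karyotype or reversion rates. The only supported size is 0.63 percentage points per relabelled subject, assuming the planned 158 per arm. The effect on the treatment comparison may be positive, negative or nil.

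**What to change.** Replace the two sentences in SAP 10.3 with:

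> Each CRc is counted in its underlying morphologic category (CR, CRi or CRp) as determined by the same assessor: the IRAC for the main analysis and the investigator for the supportive analysis. Only responses that meet all modified IWG criteria for CR, including the blast, neutrophil, platelet and red-cell transfusion criteria, enter the complete remission rate and the CR rows of displays. CRc is reported separately, split by underlying CR, CRi and CRp.

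The essential part is the first two sentences. The split of the CRc summary is what lets a reader check them.

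If the sponsor prefers to keep the pooled display, list it in SAP Section 13 and also report the CR rate without CRi- or CRp-based CRc.

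The cost is one SAP paragraph and one derivation rule, using response data already collected. If the IRAC recorded CRc as an exclusive category, the underlying category must be obtained from the IRAC, which is more work. The reported CR rate can only stay the same or fall. If the IRAC and the investigators already record CRc only on top of full CR, no result changes and the ambiguity is removed.
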